2.1. Overall Design

The original plans for the study are detailed in the following paragraphs. However, this study was stopped early. The blinding and all other aspects of this study as described below were followed through the termination announcement on November 25, 2024 and thereafter. Learnings from analyses of the sister study, PTI-125-07, were incorporated into this analysis plan.

This is a randomized, double-blind, placebo-controlled, parallel-group study of 76 weeks (19 months) duration in subjects with mild-to-moderate AD. The safety and efficacy of simufilam 50 and 100 mg tablets given twice daily will be evaluated with regard to the slowing of cognitive and

Version 1.0 | 28-Feb-2025 Page 11 of 56

functional decline in AD subjects from 50 to 87 years of age.

In this Phase 3 clinical study, approximately 1083 participants with mild-to-moderate AD (361 per arm) will receive placebo or 50 mg tablets of simufilam or 100 mg tablets of simufilam, twice daily, for 76 weeks. Randomization (1:1:1) will be stratified by low or high mini-mental state exam (MMSE) (16-20 and 21-27).

Study participants 50-87 years of age will be selected for screening based on a diagnosis of AD consistent with Stages 4 or 5 on the Alzheimer's continuum (National Institute on Aging – Alzheimer's Association 2018). Participants must have MMSE \geq 16 and \leq 27, and a Clinical Dementia Rating Global Score (CDR-GS) of 0.5, 1 or 2. Finally, participants must have confirmed positron emission tomography (PET) or fluid biomarker evidence of AD pathophysiology prior to randomization.

Once participants have been satisfactorily screened for study participation, visits to the research clinic will occur on Study Day 1 and at Weeks 4, 16, 28, 40, 52, 64 and 76.

The co-primary endpoints include:

- 1. The 12-item Alzheimer's Disease Assessment Scale Cognitive Subscale (ADAS-Cog12) and
- 2. The Alzheimer's Disease Cooperative Study Activities of Daily Living (ADCS-ADL).

[figure not shown]
Secondary endpoints include the integrated Alzheimer's Disease Rating Scale (iADRS), Neuropsychiatric Inventory (NPI), MMSE, and the Clinical Dementia Rating Sum of Boxes (CDR-SB). A brief questionnaire assessing caregiver burden, the Zarit Burden Interview (ZBI), will be collected as an additional secondary endpoint.

Safety will be evaluated by adverse event monitoring, vital signs, clinical labs, and the Columbia Suicide Severity Rating Scale (C-SSRS) at every visit. Participants will undergo magnetic resonance imaging (MRI) during screening to ensure entry criteria are met (unless a recent MRI confirms entry criteria); however, 150 subjects (50 subjects per treatment group) will also undergo repeat MRI assessments at Weeks 40 and 76 to assess both long-term safety and drug impact on brain volume as noted above. Resting electrocardiograms (ECGs) will be conducted at baseline (Study Day 1) and Weeks 4, 40 and 76. A complete physical and neurological examination will be performed at screening, and brief examinations will be performed at all other visits. Weight will be measured during the Screening Period, at baseline (Study Day 1) and at all other visits.

A limited number of research sites will be invited to participate in one or more sub-studies to assess the impact of simufilam on anatomical and biomarker endpoints, including: change from baseline in CSF biomarkers (30 subjects/group), brain volume via MRI (50 subjects/group), and amyloid and tau PET (40 and 50 subjects/group, respectively). Participants in both PET sub-studies will be required to have an MRI during the screening period and provide plasma for a biomarker sub-study. Participants in the tau PET sub-study will also provide additional plasma for a PK exposure-response analysis. Change from baseline for these imaging and fluid biomarkers represent additional secondary endpoints.

The ninety subjects (30 per group) in the CSF sub-study will undergo lumbar puncture during the Screening Period and again at the Week 76 End-of-Treatment Visit to collect CSF biomarkers.

Version 1.0 | 28-Feb-2025 Page 12 of 56

An independent DSMB will meet periodically to review participant safety assessments and determine if dosing may continue. A charter was developed with specific guidance for the DSMB.

There are no unblinded interim analyses of efficacy outcomes at any time prior to formal completion of the study and unblinding of the data.

2.2. Sample Size and Power

The sample size for this study was originally determined as follows.

Planned enrollment was approximately 1083 participants with mild-to-moderate AD. The sample size was determined by a power analysis of ADAS-Cog using data from a similar population over 76 weeks. This analysis determined that the comparison between an active arm and placebo requires group sizes of 289 to provide 90% power to detect a 45% difference from placebo at 76 weeks, based on the use of a two-sided test at the alpha = 0.05 significance level. The power calculation assumes a true mean change from baseline for placebo of 6.0 points and a standard deviation of 10.0 points. Assuming a drop-out of 20%, each treatment group should enroll approximately 361 participants.

Learnings from analyses of the sister study, and results from other development programs in AD led to change in the primary analysis population for this study to include in the primary analysis only those participants with >= 44 pg/ml P-tau181 at baseline, or other confirmation of amyloid pathology (e.g., amyloid PET). Based on results of study PTI-125-07, it is anticipated that the reduction in sample size will be offset by an increase in treatment effect such that the study will have at least as much power as originally planned.

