This statistical analysis plan (SAP) describes the planned analysis and reporting for Cassava Sciences' protocol number PTI-125-06, A phase 3, Randomized, Double-Blind, Placebo Controlled, Parallel-Group, 76-Week Study Evaluating the Safety and Efficacy of Two Doses of Simufilam in subjects with Mild-To-Moderate Alzheimer's Disease, dated 06-FEB-2023 (version 3.0). Reference materials for this statistical plan include the protocol and the accompanying sample data collection documents. Operational aspects related to collection and timing of planned clinical assessments are not repeated in this SAP unless relevant to the planned analysis.

The structure and content of this SAP provides sufficient detail to meet the requirements identified by the Food and Drug Administration (FDA), European Medicines Agency (EMA), and International Conference on Harmonization (ICH) of Technical Requirements for Registration of Pharmaceuticals for Human Use: Guidance on Statistical Principles in Clinical Trials (ICH, 1998). All work planned and reported for this SAP will follow internationally accepted guidelines, published by the American Statistical Association (ASA, 2018) and the Royal Statistical Society (RSS, 2014), for statistical practice.

The planned analyses identified in this SAP may be included in clinical study reports (CSRs), regulatory submissions, or future manuscripts. Post-hoc exploratory analyses not necessarily identified in this SAP may be performed to further examine study data. Any post hoc or unplanned, exploratory analysis performed will be clearly identified as such in the final CSR.

The statistical plan described hereafter is an a priori plan. It will be approved before any unblinded inferential or descriptive analysis of data pertaining to Cassava Science's study PTI-125-06.

This document does not include the details of the planned analyses for the external Data Safety Monitoring Board (DSMB). The schedule of planned analyses is described in the DSMB charter and separate shells for tables, listings, and figures (TLF) are prepared for the DSMB meetings.

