3.1. Study Objectives

The general objectives of this study were originally stated as: to assess simufilam's safety and to

Version 1.0 | 28-Feb-2025 Page 14 of 56

test the hypothesis that oral simufilam will slow the cognitive and functional decline in study participants with mild-to-moderate AD dementia. Secondary objectives include the assessment of simufilam's effect on neuropsychiatric symptoms and caregiver burden. A third objective is to investigate the effect of simufilam treatment on CSF, imaging, and plasma biomarkers.

The only change to this plan resulting from the early study termination is to focus on mild-to moderate AD in participants who are positive for P-tau181 at baseline or have other evidence of Amyloid pathology.

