- Censored ITT analysis set (cITT): Is the ITT analysis set with observations on and after the November 25, 2024, early termination announcement. Censored observations will be considered missing data.

Assignment of participants to analysis sets will be confirmed at a blinded data review meeting to be held before the study database is locked.

[figure not shown]
6. General Issues for Statistical Analysis

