6.1.4. Handling of Dropouts or Missing Data

[figure not shown]
The original plan was that every attempt would be made to ensure participants remain in the study to completion and all data is collected as scheduled, the occurrence of missing data cannot be completely prevented. The early study termination creates more missing data than originally anticipated. However, the administrative censoring is independent of the treatments and outcomes in this study and is therefore considered missing completely at random. Therefore, the missing data from early stopping will not bias the MMRM results.

An incomplete start or stop date of an AE or a medication will be imputed as described in section 6.1.8.

Any participant who withdraws from the study will be considered to have missing data at all subsequent visits. The primary analytic approach for efficacy assumes missing at random (MAR) to estimate what would have been observed if the participant had not discontinued. A reference-based multiple imputation sensitivity analysis (copy reference) will be employed in which missing not at random is assumed such that after discontinuation, drug-treated participants will have placebo-like values imputed for their missing data.

If up to two individual items of the total 12 items for the ADAS-Cog12 (maximum score = 80) are missing for non-cognitive reasons, the total score will be imputed by multiplying the observed score (i.e. the score for the non-missing items) by a factor that includes the maximum scores for the missing item(s) as follows:

Version 1.0 | 28-Feb-2025 Page 20 of 56

Imputed score = Observed score * (80/[80-maximum score for missing items]).

As an example, if the first item "Word Recall" (maximum score = 10) and the second item "Commands" (maximum score = 5) are missing, the observed score will be multiplied by the factor 80/(80-[10+5]) or 80/65 or 1.23. The imputed score will be rounded to the nearest integer. ADASCog12 tests with more than two missing items will be considered missing scores.

Missing items on other assessments will not be imputed; such scores will be considered missing.

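### Does the SAP's claim of undiminished power need correcting because it leaves out the Week 76 data lost to early stopping?

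*SAP*

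**What the plan says.** SAP Section 2.2 first restates the original calculation: 289 per arm for 90% power to detect a 45% difference from a 6.0-point placebo decline (SD 10.0, two-sided 0.05), raised to about 361 per arm for 20% drop-out. It then reports one change, the restriction of the primary analysis to participants with baseline P-tau181 of at least 44 pg/ml or other confirmation of amyloid pathology. Citing the sister study PTI-125-07, it says that "it is anticipated that the reduction in sample size will be offset by an increase in treatment effect" and that "the study will have at least as much power as originally planned".

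Early stopping is dealt with elsewhere. Section 2.1 says the study was stopped early and that its procedures were "followed through the termination announcement on November 25, 2024 and thereafter". Section 6.1.4 says "The early study termination creates more missing data than originally anticipated" and concludes that "the missing data from early stopping will not bias the MMRM results". The summary measure in Section 3.2 remains the difference in change from baseline to Week 76. Section 5 adds that "Assignment of participants to analysis sets will be confirmed at a blinded data review meeting" before database lock. No section gives an mITT count, a Week 76 count, the effect expected in the mITT set or a recalculated power.

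**The concern.** Two things can reduce the information at Week 76: the mITT restriction and the administrative loss of late visits. Section 2.2 sets a larger expected effect against the first only. Section 6.1.4 answers the second on bias, but data missing completely at random still cost precision. An effect increase just large enough to pay for the restriction would not also pay for the lost visits.

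This is the SAP's only power statement after termination. A reader facing a non-significant ADAS-Cog12 result could take it to mean that the trial still had at least 90% power, and read the result as stronger evidence of no effect than it is.

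**Working it through.** **Plan's own figure.** The difference is 0.45 × 6.0 = 2.7 points with SD 10. By the noncentral t, two-sided 0.05, 289 per arm gives power 0.900. Drop-out: 289 / 0.8 = 361.25, stated as 361; 3 × 361 = 1083. The plan reproduces. It concerns one ADAS-Cog comparison; no power is stated for ADCS-ADL or for success on both co-primaries.

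**Who could be affected.** The Week 76 target is Day 533 (SAP Table 2.1), which is 532 days after Day 1. Counting back 532 days from 25 November 2024 gives 12 June 2023. Section 6.1.5 windows efficacy visits to the nearest scheduled visit. The midpoint between Days 449 and 533 is Day 491, so a visit from Day 492 counts as Week 76. Counting back 491 days gives 23 July 2023. Participants who started after these dates had their Week 76 target, or the whole Week 76 window, after the announcement. No randomisation dates are given, so the share is unknown. Visits after the announcement are not excluded from the mITT analysis; Section 5 describes censoring at that date only for the cITT set.

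**Size of the loss under the planned model.** The mixed model uses earlier visits from people who lack Week 76. Assume monotone loss and correlation b^(weeks apart / 12) between visits. Let p_k be the share last seen at visit k, R_k the correlation matrix of visits 1 to k, and A_k the matrix selecting those visits. Then

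effective share = 1 / [ (Σ p_k A_k′ R_k⁻¹ A_k)⁻¹ ] at the Week 76 diagonal entry; effective n = 361 × that share.

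Assumptions not in the documents: 60% with a Week 76 value; b = 0.8 or 0.9; three patterns of loss. Difference 2.7, SD 10, no mITT loss:

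| Loss pattern | b | Effective share | Effective n | Power |
|---|---|---|---|---|
| Spread evenly over visits | 0.8 | 0.692 | 250 | 85.4% |
| | 0.9 | 0.774 | 280 | 89.0% |
| Half after Week 52, half after Week 64 | 0.8 | 0.771 | 278 | 88.9% |
| | 0.9 | 0.858 | 310 | 91.9% |
| All seen through Week 64 | 0.8 | 0.806 | 291 | 90.2% |
| | 0.9 | 0.888 | 320 | 92.7% |

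Three of the six cases exceed the planned 90%, because the plan's 289 gave no credit for the earlier visits of drop-outs. With the planned 80% at Week 76 put on the same model basis, power would be 92–93% (even loss) or 93–94% (late loss). For those patterns stopping therefore costs about 2 to 6 points: 94.0 to 91.9 at the least, 91.6 to 85.4 at the most.

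**Adding an mITT loss.** If 85% of participants qualify (assumed), the effective n values are multiplied by 0.85:

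- even loss: 212 to 238, power 79–84%
- late loss: 236 to 263, power 83–87%
- all seen through Week 64: 247 to 272, power 85–88%

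**Adding the larger effect the SAP expects.** If placebo decline in the mITT set were 7.0 (assumed), 45% slowing is 0.45 × 7.0 = 3.15 points. At the least favourable effective n, 212 to 238, power is 90–93%. A modest increase in effect could cover both losses.

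**What the results will show in any case.** At SD 10 the 95% interval half-width is 1.96 × 10 × √(2/n): 1.63 points at n = 289, 1.75 at n = 250, 1.90 at n = 212. SAP Section 4.2 commits to these intervals, and Section 7.1 to counts by analysis set and of completers.

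**The case for a change.** The strongest case for a change is that the SAP names a second loss itself, leaves it out of its only power statement after termination, and could mend this with one sentence. The textual part stands: nothing in Section 2.2 refers to stopping, and freedom from bias does not restore precision. The size could also be put higher. On the plan's own completer basis, 361 × 0.60 is about 217 per arm and power is 80%. That basis gives no credit for earlier visits, however, and the specified analysis is a mixed model that uses them.

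The rest is weaker. The 60% and 85% shares are assumptions, and the mITT loss may be small because Protocol Section 5.2 already required biomarker evidence at entry. Section 3.1 says "The only change to this plan resulting from the early study termination is to focus on mild-to moderate AD", but that sentence is about objectives, not information. The 90% was only ever for one ADAS-Cog comparison, so the feared misreading cannot extend to ADCS-ADL. A replacement sentence saying that power was not re-evaluated would assert something the documents do not establish; they show only that no calculation is reported.

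**Conclusion.** The gap is real but slight, and the plan does not need to change. Section 2.2 states an expectation and does not report a calculation. The documents cannot show it to be wrong: with an assumed 60% at Week 76 and no mITT loss, ADAS-Cog power at 2.7 points is about 85–93%. With 85% in the mITT set it is about 79–88% at an unchanged effect, and 90% or more if the effect rises to 3.15 points. These figures rest on assumed completion, correlation, loss pattern and mITT share, and on the original SD of 10.

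The trial was fully enrolled or stopped when this was written, so a revised power figure could not have altered its size. No estimate, test, alpha level or success rule draws on the sentence. Anyone interpreting a non-significant result should use the confidence interval and the number with Week 76 data, both already planned, and not a forecast of power. An analyst would do that without being told, so rewording the sentence would change no result and no sound conclusion.

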2.3. Study Population

The study population is comprised of approximately 1083 male or female participants between the ages of 50 and 87 with mild-to-moderate AD. Participants are enrolled (randomized) from approximately 78 clinical sites in the U.S., Canada, Korea and Puerto Rico.

2.4. Treatments Administered

Participants were randomized in a 1:1:1 ratio to:

- simufilam 50 mg tablets BID, or
- simufilam 100 mg tablets BID, or
- placebo tablets BID.

The randomization was stratified by baseline low or high MMSE score (16-20 vs. 21-27).

[figure not shown]
2.5. Method of Assigning Participants to Treatment Groups

The randomization schedule was computer generated by an independent statistician and randomly allocated each treatment to randomization numbers. The randomization numbers were assigned sequentially through a central interactive response technology (IRT) system as participants entered the study. The randomization was stratified as described in section 2.4.

The randomization schedule will not be revealed to participants, clinical investigators, clinical staff, study monitors, blinded statistical personnel or Cassava Sciences until all participants have completed treatment and the database has been finalized and locked.

Participants who discontinue from the study or are terminated will not be replaced.

Version 1.0 | 28-Feb-2025 Page 13 of 56

The IRT system will be used throughout the study for screening, randomization, study drug dispensation and management, and emergency unblinding. Individual participant treatment is automatically assigned by the IRT at baseline (Study Day 1) to participants who meet all entry criteria. The participant's randomization number is a unique number corresponding to the treatment allocated to the participant.

At each dosing visit, the site will access the IRT system and enter the necessary participant-specific information. For randomized participants, this information is used by the IRT system to dispense the correct dose and amount of study drug in a uniquely numbered bottle.

2.6. Blinding and Unblinding

All participants, investigators, and study personnel, including but not limited to sites, the Sponsor and Premier Research will be blinded to treatment assignment and receipt of study drug during the conduct of the study, through database lock. The treatment assignment will not be unblinded during the conduct of the study except in emergency situations where the identification of the study drug is required for the safety of an individual study participant. The investigator should make every effort to contact the medical monitor prior to individual participant unblinding or as soon as possible after unblinding without making the medical monitor aware of the treatment assignment.

If a treatment assignment is unblinded, the date and name of the person who was unblinded, and the reason for unblinding, are recorded in the appropriate source documents. The participant will be discontinued immediately from the study but will be followed up as required by standard medical practice. Unblinding will be managed via the IRT system.

Prior to unblinding, data that may functionally unblind personnel, including PK and biomarker results, will be handled with diligence. Any data that may unblind study personnel or the study team will be presented in blinded fashion only or withheld until after study unblinding.

The blinding of all study participant data will be maintained following the announcement on November 25, 2024, to discontinue this study until data lock.

2.7. Schedule of Events

The conduct of the study and different procedures performed from Screening Visit to End of Study Visit will be as per the visit schedule provided in Appendix A – Schedule of Activities.

2.8. Administration of Study Drug to Participants

[figure not shown]
Simufilam or placebo tablets will be supplied in 70-count bottles for a 4-week supply or 188-count bottles for a 12-week supply. Each bottle will contain 7 or 10 days of extra medication to accommodate scheduling flexibility with clinic visits. Each bottle is labeled with a unique double-blind identification (ID) number that is randomly assigned to a treatment. A computer-based clinical study management (i.e., IRT) system will specify the bottle ID number to be dispensed according to the participant's treatment randomization.

3. Study Objectives and Endpoints

3.1. Study Objectives

The general objectives of this study were originally stated as: to assess simufilam's safety and to

Version 1.0 | 28-Feb-2025 Page 14 of 56

test the hypothesis that oral simufilam will slow the cognitive and functional decline in study participants with mild-to-moderate AD dementia. Secondary objectives include the assessment of simufilam's effect on neuropsychiatric symptoms and caregiver burden. A third objective is to investigate the effect of simufilam treatment on CSF, imaging, and plasma biomarkers.

The only change to this plan resulting from the early study termination is to focus on mild-to moderate AD in participants who are positive for P-tau181 at baseline or have other evidence of Amyloid pathology.

3.1.1. Primary Objective

The original primary objective was stated as: to assess simufilam's effect on the co-primary endpoints of ADAS-Cog12 and the ADCS-ADL, baseline to the end of double-blind treatment (Week 76). The early termination of the study did not change the primary objective.

